The primary outcome will be change in degree of facial movement during different facial expressions as described above pre- and post-study. The secondary outcome will be any improvements in quality of life pre- and post-study as captured by the Facial Disability Index. The Facial Disability Index will be used as a validated quality of life instrument [12]. See Appendix M. Although it is somewhat dated (1996) and it was intended for use with facial neuromuscular disorders and facial palsy, its questions were deemed the most relevant for this study after thorough review of available burn, facial palsy and general quality of life measures.

The subjects will not be responsible for any research-related costs; insurance companies will not be billed. Validated parking will be offered if attending visits in person.

5. Sub-Study Procedures:

Not applicable.

6. Criteria for Inclusion of Subjects:

We plan to recruit 20 adult or pediatric patients who have sustained facial burns or who have sustained a facial injury resulting in scarring, tightness, limited range of motion of facial skin or musculature or fibrosis and are in the chronic phase of recovery to complete the 8 week treatment.

1. Age 7-80
2. Male or Female Sex
3. Patients who have sustained a facial burn and are now in the chronic phase, or any patient experiencing facial tightness or limited range of motion due to other problems, including patients s/p radiation to the head and neck, trauma, scarring and scleroderma
4. Chief complaint(s) of limited mouth opening, difficulty chewing or speaking, decreased range of motion for oral structures, and/or limited facial expressions
5. Subject or caregiver (parent or guardian, in case of pediatric population) must be able to give informed consent
6. Subject or caregiver (parent or guardian, in case of pediatric population) must be able to perform exercises at home and must be able to record time spent using the devices.
7. Participants who are undergoing other treatment methods such as use of compression garments, skin grafting, radiation or other facial surgery, etc must suspend all of these treatments for the duration of the 2 month trial.
8. Internet access including access to FaceTime, Skype or Zoom and email access if electing telehealth option for enrollment

7. Criteria for Exclusion of Subjects:

The following will exclude patients from participation in the study:

[name] and [name]

Version 10/October 2020

Page 9 of 24

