Expected benefits include: increasing range of motion for multiple facial muscles and tissues; reducing the impact and appearance of scar tissue; ability to target multiple sites across the face, with particular attention to the cheeks, nasolabial folds, upper lip, mentolabial junction and modiolus; achieving a stretch that currently available tools cannot provide; improved ability to produce different facial expressions; increased speech intelligibility; improved ability to complete oral hygiene.

14. Biostatistics:

Sample size calculation shows that a sample size of 20 (accounting for 10% missing rate) will be able to detect an effect size of 0.7 by using a two-sided paired t-test, if the real study has statistical power of 0.8 and the significance level (alpha) is 0.050.

Descriptive statistics for continuous and categorical variables will be presented as mean \pm SD and quartiles, and frequencies and proportions, respectively. For the weekly measurements, we will use the descriptive statistics and individual trend plots to present the data. The primary outcome is the change in millimeters after the completion of treatment (post – pre measures) for each facial expression. We will use paired t-tests (if data is normally distributed) or non-parametric alternatives (e.g., Wilcoxon signed-rank test) to test if the changes are statistically significant. The change score of facial disability index (FDI) will be analyzed using the same method. The pre-post outcome of the cranial nerve assessment will be classified by categories (Pass-

Pass, Fail-Pass, Fail-Fail), and the frequencies and proportions will be reported. Two-sided statistical significance will be considered for alpha at the 0.05 level for all tests.

References:

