Appendix I

Example patient documentation handout – see separate document for complete form with header/footer

Easy Stretch Toolkit

Who placed the tools? Circle one: patient/caregiver

Tool (size and color): _____ Placement location*: _____

*See attached picture.

Date	AM – Number of minutes used	PM – Number of minutes used

Appendix J – Cranial Nerve Assessment form - see separate document for complete form with header/footer

Easy Stretch Toolkit
Cranial Nerve Assessment: Oral Motor / Facial Measurements

Nerve	Task	Comments	Initial Exam Pass/Fail	Final Exam Pass/Fail
CN I Olfactory	Smell orange peel			
CN III Oculomotor	Follow the finger			
CN IV Trochlear	"H"			
CN V Trigeminal	Ophthalmic – brush across forehead			
	Maxillary – cheekbone			
	Mandibular- chin			

[name] and [name]

[figure not shown]
Version 10/October 2020

Page 18 of 24

	Corneal Reflex Test			
	Masseter /Temporalis–clench teeth			
	Jaw Jerk			
CN VII Facial	Crease forehead			
	Close eyes			
	Close eyes against resistance			
	Puff out cheeks			
	Smile and show teeth			
CN IX Glossopharyngeal	Gag reflex			
CN X Vagus	Say "ah"			
CN XI Accessory	Sternocleidomastoid and traps –			
	Head turn against resistance			
	Shoulder shrug - resistance			
CN XII Hypoglossal	Motor to muscles – Stick out tongue			

Week #: 1 Completed on ____ / ____ / ____ Time: _____ By: _____
 Week #: 12 Completed on ____ / ____ / ____ Time: _____ By: _____

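### The planned cranial nerve table has no Pass-Fail category, so it can show improvement or no change but not worsening

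*Combined protocol and SAP*

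**What the plan says.** Section 14 introduces the summary with "The pre-post outcome of the cranial nerve assessment will be classified by categories". The bracketed list that follows is Pass-Pass, Fail-Pass and Fail-Fail. A page break falls inside the first item, and the text after the break reads "Pass, Fail-Pass, Fail-Fail), and the frequencies and proportions will be reported". No test is attached to this table.

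The data come from the form in Appendix J. Each task has one column headed "Initial Exam Pass/Fail" and another headed "Final Exam Pass/Fail".

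The Measuring Outcomes part of Section 4 fixes the standing of this table: "The primary outcome will be change in degree of facial movement during different facial expressions". The secondary outcome is quality of life on the Facial Disability Index. The cranial nerve assessment is neither.

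One side matter: the form's second completion line begins "Week #: 12 Completed on", whereas Sections 3, 4 and 6 describe an 8-week or 2-month study and no week-12 visit.

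**The concern.** Two binary ratings taken in sequence have four possible outcomes. The plan names the two that mean no change and the one that means improvement. It gives no place to a participant who passes a task at the start and fails it at the end.

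The study has no comparison group: Section 3 makes each patient his or her own control, and Section 2 says the product has not been studied before. A before-and-after summary in that setting should be able to show change in both directions. Several Appendix J tasks concern the face and jaw (puffing out the cheeks, smiling, clenching the teeth), and Section 10 lists asymmetrical range of motion among the risks. The documents do not say whether that would turn a Pass into a Fail, but nothing in them rules deterioration out.

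At stake is a table that looks favourable by construction. An analyst who follows the list literally must drop a worsened result, put it in the wrong category, or publish proportions that do not add up.

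**Working it through.** **Is the list really closed?** The page break separates the two halves of Pass-Pass. The sentence runs on across it, the items are separated by commas, and the bracket closes after Fail-Fail. No wording marks the list as examples, although the same paragraph does mark an example when it names the Wilcoxon test. No other section supplies a fourth category.

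**Categories against possible outcomes.** Initial exam (2 levels) × final exam (2 levels) = 4 pairs.

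| Initial | Final | Meaning | Listed in Section 14 |
|---|---|---|---|
| Pass | Pass | no change | yes |
| Fail | Pass | improved | yes |
| Fail | Fail | no change | yes |
| Pass | Fail | worsened | **no** |

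So 4 − 3 = 1 pair has no category. The form can record it; the gap is in the planned table, not in data collection.

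**Denominators.** Section 14 gives a sample of 20, "accounting for 10% missing rate", hence 20 × 0.90 = 18. This agrees with the plan's own sample size: a two-sided paired t-test with 18 pairs, effect size 0.7 and alpha 0.05 has power 0.799 (noncentral t), and 18 / 0.90 = 20. That allowance was made for the t-test, so using 18 for the cranial nerve form is an assumption.

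**Size of one Pass-Fail result.** Section 14 does not name the unit. The row layout of Appendix J points to one distribution per task.

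- Per task row: 1/20 = 5.0%, or 1/18 = 5.6%. The three listed proportions then sum to 19/20 = 95.0%, or 17/18 = 94.4%.
- If the worsened participant is left out of N, the three sum to 100% of 19 or 17, and the worsening is not visible.
- If all tasks were pooled instead (19 or 20 rows, depending on whether the sternocleidomastoid and trapezius line is scored): 1/(20 × 20) = 0.25% to 1/(18 × 19) = 0.29%.

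Pass-Fail is missing under either unit.

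**Illustration with assumed counts.** Take one task row with 18 assessed, 2 Fail-Pass and 2 Pass-Fail. Net change is 2 − 2 = 0. The table would show improvement of 2/18 = 11.1%, or 2/(18 − 2) = 2/16 = 12.5% if worsened results are removed from N, and no worsening.

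**The case against.** The strongest reply is that the gap has an effect only if a Pass-Fail result occurs; if none does, the three categories are complete. The documents give no rate, so this stands, and it is a reason to rate the point low.

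A second reply is that the missing count could be recovered. Frequencies are to be reported as well as proportions, so Pass-Fail equals N minus the three listed counts, provided N is the number assessed at both exams. Section 14 does not define N for this table, so a remainder could not be told apart from participants without a final exam. Tabulating the initial and final columns separately might also help, but the plan does not say that this will be done.

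Third, the percentages depend on a per-task reading and on an assumed 18. This is fair. The pooled reading gives a far smaller percentage, and the number assessed per row is uncertain because visits may be held by telehealth and the documents do not say how tasks such as the gag or corneal reflex would be examined remotely. The omission itself depends on none of this.

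Fourth, worsening might appear through the adverse event reporting in Section 11. It might, but no text links a failed final exam to an adverse event, and such a report would not repair the table.

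Finally, the week-12 label has no bearing on the categories. That is correct; it adds no weight here.

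**Conclusion.** The concern holds as a minor one. Section 14 specifies a closed list that covers three of four possible results and leaves out the only unfavourable one. On the per-task reading, each worsened result in a row takes 5.0% (N = 20) to 5.6% (N = 18) out of the listed categories, or disappears if it is removed from N. These figures rest on the row-by-row reading of Appendix J and, for 18, on carrying over the 10% missing allowance. No frequency of worsening is asserted.

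The consequences are limited. The table is descriptive, and neither the primary nor the secondary analysis, the sample size nor the alpha level depends on it. The raw forms would still hold the worsened results.

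**What to change.** In Section 14, add Pass-Fail (worsened) to the category list. Add one sentence stating that all four categories will be reported for each Appendix J task as n/N, where N is the number of participants assessed on that task at both exams. If the team prefers another reporting unit, it should name it; the fourth category is needed either way.

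Separately, as housekeeping, reconcile the week-12 completion line in Appendix J with the 8-week schedule in the body. The appendix refers to a fuller version of the form ("see separate document for complete form with header/footer"), so that document should be checked at the same time.

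The cost is one category and one sentence in Section 14, and one label to reconcile. Sample size, alpha, visits and staffing do not change.

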Appendix A

Example Prototypes

Appendix B – Nuk brush

Appendix C – Beckman Oral Probe

Appendix D – Chewy Tubes

Appendix E – Orastretch

[figure not shown]
Appendix F - Therabite

[figure not shown]
Appendix G

Intended facial placements for the Easy Stretch Tools. Each shape has its own targeted intraoral placement.

[figure not shown]
Circle tool

Bar tool

L shape tool

Appendix H – see separate document for complete form with header/footer

Easy Stretch Weekly Visit Summary

Homework completed: yes/no

Obtained copy of HW record: yes/no

Current Tool Placement:

Yellow	#1	#2	#3
Blue	#1	#2	
Green	#1	#2	#3

Patient Comments:

Patient verbalizes wish to continue in the study: yes/no

[name] and [name]

Version 10/October 2020

Page 16 of 24

Pictures taken	Check as completed
At rest	
Wrinkle the nose	
Gentle smile	
Broad smile with lips closed	
Broad smile with teeth together	
Vocalize prolonged “eee” sound	
Vocalize prolonged “ooo” sound	
Lip pucker – drink from a straw	
Open mouth wide	
Side profile	

Next Tool Placement:

Yellow	#1	#2	#3
Blue	#1	#2	
Green	#1	#2	#3

Follow up visit date/time: _____

Date/Time this assessment was completed: _____

Signature of principal and/or co-investigator: _____

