Easy Stretch Toolkit: A Pilot Study

Co-Investigators: [name] and [name]

Funding Sponsor: UTMB Health Technology Commercialization Program

Version 10/October 2020

Efficacy of the Easy Stretch Toolkit: A Pilot Study

1. Introduction and Purpose:

The Easy Stretch Toolkit (patent pending) is a set of three novel intraoral tools designed to deliver a passive stretch to scarred or contracted orofacial musculature, with the goals of: 1) increasing measurable range of motion for multiple facial muscles and tissues, and 2) reducing the impact and appearance of scar tissue. We designed the Easy Stretch Toolkit for patients negatively impacted by facial burns. We propose a pilot study to test if the tools can directly target multiple sites across the face, with particular attention to the cheeks, nasolabial folds, upper lip, mentolabial junction and modiolus, achieving a stretch that currently available tools cannot provide. We hypothesize that there will be an expected gain of improved ability to increase use of orofacial musculature, as well as improved range of facial expressions and related motor functions in patients with facial burn injury. The Easy Stretch Toolkit is proposed for use with adults and children over the age of 7 in this pilot study. Use of the device(s) is intended to be utilized by a trained Speech Pathologist. The exact tool to be used will be selected by the Speech Pathologist based on the patient's specific deficit areas and needs. In this pilot study, investigation into the efficacy of the Toolkit will be limited to subjects with chronic facial burns, with future plans to expand the project to subjects of all ages in the acute healing phase if preliminary results prove the tools are effective. Physical prototypes were created with the assistance of the MakerHealth Space Lab at UTMB, following the designs and initial prototypes of the creators (patent pending). See Appendix A. The current treatment options for patients with scars secondary to orofacial burns are discussed in the Background and pictures of tools are shown in Appendix B-F. Because our tools are similar, and in some ways potentially safer than the current tools available in the market, we believe that the Easy Stretch Tools are a minimal risk device. This product represents an advance in the care of these patients. There is minimal risk associated with correct use of the product (discomfort from stretching, bleeding if facial burn sites are not fully healed, possible allergy from intraoral contact with food-grade silicone, remote choking risk, asymmetrical range of motion, remote tearing of the mucous membrane); the expected benefits are that the tools will increase mobility of the orofacial skin and musculature, as well as reduce and possibly prevent burn-induced scar formation. This protocol and enrollment procedures are revised due to the Covid -19 Pandemic to allow for increased ability to enroll participants due to the University's restrictions on travel.

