The Toolkit is not currently available to the general population and the current project will be the first time this product has been studied. We, the investigators and the creators posit that the Easy Stretch Toolkit will be applicable for neonate, pediatric and adult burn victims. This trial will include the adult and pediatric burn population. If this clinical trial is successful, our goal would be to expand to children under the age of 7, including the neonate population and ultimately to market, mass produce and sell the product to all patient populations, including patients with acute burn injuries. We would plan to conduct a larger trial (with a power analysis after we determine effect sizes) to further investigate efficacy of the Easy Stretch Toolkit. The need for early intervention in facial scar management was documented by Parry et. al. and Clayton et. al. [1,6]. In the future, another focus would be on the early use of these devices as a method for both preserving and increasing range of motion and elasticity in patients immediately following a burn injury. Additional target populations include patients with lip contractures following cleft lip surgery, as well as research into use of the Toolkit as an oral stimulation device for use in the NICU population. Use of the Easy Stretch Toolkit with each of these populations will need to be researched and studied by the creators; we plan to submit amendments to this parent protocol to include additional patient populations and indications in the future.

3. Concise Summary of Project:

Our proposed study and design is intended to study two Aims:

- 1) To determine whether use of the devices results in measurable change in range of motion and quality of life via pre- and post-use data and measurements for orofacial movements and function.
- 2) To develop an effective prescriptive rehabilitative plan for orofacial scar management for the patient to follow including an 8 week active treatment period.

Experimental Device:

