The investigators would like to request a waiver of written consent to verbally screen potential subjects via phone, electronic media or in person using the eligibility checklist and inclusion/exclusion criteria, prior to their first visit when they will sign the consent document. Because the investigators are pursuing multiple recruitment avenues apart from chart review, a flexible screening process is necessary.

At the time of the initial contact with the patient, a full description of the study will be provided. Consent will be obtained prior to or at the beginning of the first treatment session. In the case of a pediatric subject, verbal assent will be obtained for children ages 7-12 and written assent will be obtained for children ages 13-17. Parental permission will be obtained via the consent form as parent/guardian is now included as part of that consent form.

At the time of consent a detailed medical history form and written consent for participation will be obtained by the investigators. A copy of the consent form will be mailed to the subject. Ongoing participation in the study will be reviewed during the weekly visits. Subjects will be scheduled for an immediate start date.

10. Potential Risks:

Adverse effects are not expected. However, potential risks include possibilities for: discomfort from stretching, bleeding if facial burn sites are not fully healed, allergy from intraoral contact with food-grade silicone, asymmetrical range of motion, and possible tears through the burned skin. The handle is designed to reduce the risk of choking as the subject or caregiver should be holding onto the device when using it. However, there is a remote choking risk if the subject uses the device incorrectly (such as chewing on the device, sucking on the device or removing the head of the device from the handle).

11. Subject Safety and Data Monitoring:

The PI will review the safety of these interventions with [name], Faculty Sponsor, at 6 month intervals. Significant problems related to insertion of the device such as bleeding, choking will be reported to the IRB immediately. Any related or unrelated adverse events will be reported in a timely manner to the IRB.

12. Procedures to Maintain Confidentiality:

Pictures will be taken using a departmental iPad and patient data will be stored on secure UTMB computers. Patient's written or verbal consent will be obtained prior to photographing the patient.

13. Potential Benefits:

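### Neither the weekly form nor the daily log asks about the named risks, and Section 14 plans no adverse-event table, although Section 11 requires adverse events to be reported

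*Combined protocol and SAP*

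**What the plan says.** **Reporting duty.** Section 11 (Subject Safety and Data Monitoring) states: "Any related or unrelated adverse events will be reported in a timely manner to the IRB". It also calls for immediate notification of significant insertion-related problems such as bleeding or choking, and a safety review every 6 months.

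**Named risks.** Sections 1 and 10 both list discomfort, bleeding, silicone allergy, asymmetrical range of motion and choking. They differ on tears: Section 1 has "remote tearing of the mucous membrane", while Section 10 has "possible tears through the burned skin". Section 10 also mentions the head being removed from the handle.

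**Collection.** Appendix H covers homework, current and next tool placement, the wish to continue and a photograph checklist, plus the line "Patient Comments". Appendix I covers who placed the tool, which tool, where, the date and the morning and evening minutes. The Appendix Legend lists no adverse-event form.

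**Analysis.** Section 14 covers change in facial measurements, the Facial Disability Index and the pre-post cranial nerve result. The cranial nerve categories given are Pass-Pass, Fail-Pass and Fail-Fail. No adverse-event summary is described.

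**Setting.** Section 2 says that "the current project will be the first time this product has been studied". Section 4 proposes sessions of about 60 minutes twice daily for 8 weeks, with weekly contact in person or by telehealth. Telehealth is open to all participants from age 7.

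**The concern.** An event has to be found before it can be reported. Section 11 sets the duty to report, but no visible form contains a question that would find the events, and no planned analysis would count them.

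The device is new and is used largely at home by the participant or a caregiver. As proposed, use amounts to 2 hours a day for 56 days, or 112 hours per participant. Several named risks can occur and resolve between weekly contacts, or leave no mark on a photograph of a facial expression. If they are recorded mainly when mentioned, the count will probably be too low, and the 6-monthly review can consider only what was collected.

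Sections 1 and 2 say that, if results are good, the sponsor would like to move on to acute burns and to children under 7, including neonates. A count of harms from a standard question, with its uncertainty, is among the most useful things this pilot could supply for that decision.

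**Working it through.** **1. The plan's own sample size.** Section 14 says the sample can "detect an effect size of 0.7 by using a two-sided paired t-test", with "statistical power of 0.8 and the significance level (alpha) is 0.050", and allows 10% missing.

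- Exact noncentral-t power for a paired t-test at effect size 0.7 is 0.799 with n = 18 and 0.823 with n = 19.
- 18 / 0.9 = 20, so the stated 20 reproduces. Taking 19 for power strictly above 0.80 gives 19 / 0.9 = 21.1, or 22.
- This figure is for efficacy. Nothing in Section 14 concerns precision for harms.

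**2. Named risks against the places where they could be recorded.**

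| Risk (Sections 1 and 10) | Asked in Appendix H or I? | Other route in the plan |
|---|---|---|
| Discomfort | No | Free comment |
| Bleeding | No | Free comment; may be seen at a visit |
| Mucosal tear (Section 1 only) | No | Free comment; may be hidden inside the mouth |
| Skin tear (Section 10 only) | No | Free comment; may be seen or photographed |
| Allergic reaction | No | Free comment; may have resolved by the visit |
| Choking, detached head | No | Free comment |
| Asymmetry | No | Right and left distances in Section 4 |

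Only asymmetry has a planned measurement.

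**3. What 20 participants can show with full capture.** Let p be the true per-participant risk.

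- Chance of at least one affected participant: 1 − (1 − p)^20. At p = 1%, 1 − 0.99^20 = 18%. At 5%, 1 − 0.95^20 = 64%. At 10%, 1 − 0.90^20 = 88%.
- Upper limit after zero events, two-sided 95%: 1 − 0.025^(1/20) = 16.8%. One-sided 95%: 1 − 0.05^(1/20) = 13.9%.
- With 18 participants, the limits are 18.5% and 15.3%.

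**4. Illustration of incomplete capture.** The documents give neither an event rate nor the share of affected participants whose event would be recorded. Let that share be s, an assumption. The chance of at least one recorded event among 20 is 1 − (1 − sp)^20.

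| True risk | s = 100% | s = 50% | s = 25% |
|---|---|---|---|
| 5% | 64% | 40% | 22% |
| 10% | 88% | 64% | 40% |
| 20% | 99% | 88% | 64% |

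After zero recorded events, the limit on the true risk is the full-capture limit divided by s. At s = 50% the two-sided limit becomes 16.8% / 0.5, about 33.7%, and the one-sided limit 13.9% / 0.5, about 27.8%.

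**5. Cranial nerve categories.** Appendix J scores each item pass or fail at an initial and a final examination, which gives four combinations. Section 14 names three. The one left out is Pass-Fail, the only one that represents worsening.

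**The case against.** The strongest reply is that participants are not left to complain unprompted. Section 4 rests subject safety on training and weekly one-to-one contact with a Speech Pathologist, and each week nine expressions, including open mouth, and a profile are photographed. A clinician who sees the face weekly may notice bleeding or a skin tear. Asymmetry can be read from the four paired right and left distances. This stands, so a reader who infers that safety rests entirely on volunteered complaints goes too far. What remains is that the stated purpose of the contact is appropriate use, that no dedicated field records a harm that is noticed, and that events between visits may leave nothing to see.

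A reader might also infer that the trial cannot support its minimal-risk statement. The documents do not support that as a criticism. Section 1 argues minimal risk in advance, from similarity to marketed tools, and neither aim in Section 3 tests it. Twenty participants could not establish it even with perfect collection, as the 16.8% limit shows.

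Nor is adverse-event reporting absent, because Section 11 requires it. The gap is in finding and tabulating events. The plan also does not say what share of participants will use telehealth only, so no weight should be put on that share.

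Two cautions remain. The capture shares are assumptions, applied once per participant without modelling repeated weekly contacts. And Appendix H points to a separate complete form. It is described only as adding a header and footer, but if it contains harm items, the form part of this point falls away. The gap in Section 14 would remain.

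**Conclusion.** The point holds in a limited form. The printed weekly form and daily log contain no question about the named risks, and Section 14 plans no adverse-event table, although Section 11 requires related and unrelated events to be reported. Followed as written, less visible events between visits would be recorded mainly if mentioned, and the trial would plan no estimate of how many participants had them.

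The limit that can be stated without assuming a capture rate is modest: zero events in 20, with everyone asked, leaves rates up to 16.8% not excluded (two-sided 95%). The fall from 88% to 64% at a true risk of 10% illustrates the direction of the loss; it is not an estimate of it. The efficacy sample size is unaffected. The change is worth making because it is cheap and bears on participant safety in the first study of the device. The conclusion assumes that the separate version of Appendix H has the same content as the printed one.

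**What to change.** **Appendix H.** Add a standard question at baseline and at every weekly visit, with a yes/no line for each of: pain or discomfort, bleeding, mucosal tear, skin tear, allergic reaction, choking or detached head, and other. At baseline, record what is already present; at later visits, ask whether it is new or worse since the last visit. Participants enter with tightness, scarring or restricted movement and there is no control group, so without the baseline entry pre-existing problems would be counted as device events. Assess asymmetry from the right and left distances already planned.

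**Sections 1 and 10.** Reconcile the two risk lists so that both kinds of tear are covered.

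**Section 14.** Add a table of the number and percentage of participants with each event, with exact two-sided 95% confidence intervals. The denominator should be all participants who used the device, including those who leave early. Add Pass-Fail to the cranial nerve categories.

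**Cost.** Slightly longer visits, one extra table and a small form revision. The reported number of minor events will probably rise, and the report should say that events were actively asked for.
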